8.3 Exclusion Criteria

Subjects will not be included in the study if any of the following criteria applies:

- Intake of any prescribed medication within 2 weeks of the beginning of the study
- Intake of any food supplements within 2 weeks of the beginning of the study, except vitamin D and calcium
- Hypotension
- Any clinically significant history of serious digestive tract, liver, kidney, cardiovascular or hematological disease, diabetes
- Gastrointestinal disorders or other serious acute or chronic diseases
- Known lactose/gluten intolerances/ food allergies (limitation for standardization of meals)
- Inadequate veins (in the opinion of the investigator) or known contraindication to placement of a dedicated peripheral line for venous blood withdrawal
- Known drug and/or alcohol abuse
- Using any form of nicotine or tobacco
- Mental incapacity that precludes adequate understanding or cooperation
- Participation in another investigational study or blood donation within 3 months prior to or during this study

	Study Title	Bioavailability Study of COQUN ORAL FORMULATION (CoQ10) administered in Healthy Adults (CoQ10-01)		
	Study ID	VF-BAQ10/2018	Sponsor:	VISUFARMA SpA
	Date	March 03, 2018	Vers.	Final

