10.5 Conduct of the Study

10.5.1 Screening visit & treatment start (V1, Day -7, single dose phase)

Screening visit will be performed once the subject signed the informed consent form and the following procedures will be performed:

- subject information and informed consent
- demographic data and medical history recording
- physical examination
- vital signs (blood pressure, heart rate, temperature and respiratory rate)
- body measurements (height and weight)
- 12 lead ECG
- safety laboratory analysis
- concomitant medication recording

	Study Title	Bioavailability Study of COQUN ORAL FORMULATION (CoQ10) administered in Healthy Adults (CoQ10-01)		
	Study ID	VF-BAQ10/2018	Sponsor:	VISUFARMA SpA
	Date	March 03, 2018	Vers.	Final

- assessment of inclusion/exclusion criteria

Once the subjects are considered eligible for the study, all 24 adult healthy subjects will enter the single dose treatment phase and will be given a dose of 100 mg of COQUN ORAL FORMULATION and plasma coenzyme Q10 will be measured over the next 12 hours: at 1, 2, 4, 8 and 12 hours after intake. Pharmacokinetic properties including area under the curve (AUC), maximum plasma concentration (Cmax), time to maximum plasma concentration (Tmax) and elimination half-life (t 1/2) will be measured.

Safety parameters will be monitored during the whole day.

The subjects will be requested to fasten for at least 10 hours before IP intake; when will arrive at the study center subjects will be hospitalized for at least 12 hours for the single dose phase, therefore subjects will remain at site for around 24 hours.

At the end of this visit, if no SAE occurs, subjects will be dismissed and will be requested to return after 1 week for the second study visit and multidose phase start.

In the wash-out period subjects will have to respect the same lifestyle regimen and no medication shall be taken, if not necessary.

Subjects will be given a diary and will be requested to report any possible adverse event experienced between V1 and V2, as well as any treatment taken for treating an AE, if applicable.

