10.6.10 IP administration

IP will be administered at site by the subject on Day -7 by intake of 1 IP capsule of 100mg, under investigator's supervision.

Subjects should be fasted for at least 10 h prior to and 2 h after administration. Water will not be permitted 1 hour before dosing dose and 1 hour post dosing.

Per protocol IP dose is 100mg.

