10.6.11 Pharmacokinetic assessments

Pharmacokinetic parameters will be assessed in serum. For pharmacokinetics analyses blood samples will be collected for the analysis of plasma coenzyme Q10 before dosing and over the

	Study Title	Bioavailability Study of COQUN ORAL FORMULATION (CoQ10) administered in Healthy Adults (CoQ10-01)		
	Study ID	VF-BAQ10/2018	Sponsor:	VISUFARMA SpA
	Date	March 03, 2018	Vers.	Final

next 12 hours: at 1, 2, 4, 8 and 12 hours after intake on the single dose period (day -7) and at each following ambulatory visit.

4 ml of blood will be collected in blood collection tubes. Each blood sample will be allowed to clot for 20-25 minutes at room temperature. Then they will be centrifuged for 15 minutes at 1300g at 4°C. Afterwards the plasma will be separated into the secondary sample tubes as follows: 0.5 ml plasma into two cryotubes, one to be send to the pharmacokinetic laboratory and one back-up. The plasma cryotubes will be appropriately labeled (study code, treatment period, subject number, sampling time) and stored at -20°C to -80°C at the study center until shipment to the specified laboratory. The backup cryotubes will be kept at the study center at least until the confirmation from the pharmacokinetic laboratory that the samples arrived in good conditions.

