4.4 Study periods, Baseline and Endpoint Values

- First date of medication administration

Day 1 date (collected in patients' V2-V5 diary) will be treated as first intake of study medication.

- Last date of medication administration

Day 28 date (collected in patients' V2-V5 diary) will be treated as last intake of study medication (if the subject completes the study this date should coincide with the date of last investigational product intake).

If the date of last intake of study medication is not available, due to premature termination or other reasons, date of last investigational product intake (collected in the end of study form of the CRF) will be imputed.

- Duration of study medication treatment

Duration (days) = Date of last medication administration - Date of first medication administration + 1

- Baseline value

The baseline value for a variable is defined as the last non-missing value collected before first study medication administration. In the single dose phase, the moment 0 (visit 1- hour 0) will be considered as baseline value while in the multidose phase, baseline will be visit 2 (day 0) if not specified otherwise.

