	Statistical Analysis Plan	Page	Page 22 of 69
		Effective Date	07/05/2018

Analysis of Primary Efficacy variable:

Descriptive statistics such as mean \pm standard deviation, median with interquartile range, minimum, maximum and coefficient of variation will be presented for the plasma concentration of coenzyme Q10 at each time point in the entire sample of subjects. 95% confidence interval will be provided as well.

An explorative analysis on gender will be performed showing descriptive statistics for plasma concentration of coenzyme Q10 by gender. The effect of gender will be explored by means of a mixed model for repeated measures with covariates *gender*, time and the interaction term *gender*time*.

Descriptive statistics will be also provided for the plasma concentration of coenzyme Q10 at each time point by treatment group.

Change of plasma concentration versus baseline (i.e. change versus visit 2 values) will be computed for each study visit both for the whole sample and by treatment group.

Change will be computed in the following way:

$$\text{Change (\%)} = \frac{\text{Value at Visit X} - \text{Baseline Value}}{\text{Baseline Value}} \times 100$$

Area under the curve, maximum concentration in the plasma, time of maximum concentration and terminal half-life will be presented descriptively on the original scale.

95% confidence interval will be provided for the means of 100mg OD and 100mg BID for COQUN ORAL FORMULATION for the parameters AUC_t , C_{max} , T_{max} and terminal half-life. A Student t-test for unpaired data will be performed in order to detect differences between the two groups in the pharmacokinetics parameters.

A concentration by time graph will be presented for the multidose phase by treatment group in order to have a graphical visualization of the pharmacokinetics properties over time.

Line graphs will be provided for the concentration of coenzyme Q10 in the whole sample and by gender.

In performing statistical analysis, it is important to assess the statistical outliers. In fact, inclusion or exclusion of outlying subjects may lead to a different conclusion in assessment of differences in bioavailability between two formulations. It is therefore important to identify these outliers and study their effects.

Primary endpoint will be evaluated on the ITT population and analysis will be replied on the PP population. Results obtained on the PP population will be considered as supportive of those obtained on the ITT set.

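### The documents disagree on whether CoQ10 is measured before the Day -7 dose, and no planned estimate compares that level with V2, the multidose baseline taken 7 days after a study dose

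*SAP*

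**What the plan says.** **Pre-dose sample.** Protocol 10.6.11, the section on PK sampling, states that "blood samples will be collected for the analysis of plasma coenzyme Q10 before dosing" as well as afterwards. SAP 4.3 defines V1-H0 as the assessment before intake, SAP 5.2.3 says concentration is recorded there, Tables 25 and 26 have H0 rows, and Table 27 reports changes from H0. Protocol 10.5.1, which tells the site what to do at V1, says only that "plasma coenzyme Q10 will be measured over the next 12 hours: at 1, 2, 4, 8 and 12 hours after intake". The synopsis, Protocol 10.3 and SAP 4.5 give the same five post-dose times. In the flow chart (Protocol 3.2) the Pharmacokinetics row is blank at moment 0 and marked in the other nine columns.

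**Baseline.** SAP 4.4 first gives a general rule: "The baseline value for a variable is defined as the last non-missing value collected before first study medication administration". The next sentence sets one baseline per phase and names V2 for the second: "In the single dose phase, the moment 0 (visit 1- hour 0) will be considered as baseline value while in the multidose phase, baseline will" (the quote stops just short of naming V2). The same section says "Day 1 date (collected in patients' V2-V5 diary) will be treated as first intake of study medication". All subjects have by then had a study dose: "IP will be administered at site by the subject on Day -7 by intake of 1 IP capsule of 100mg" (Protocol 10.6.10). SAP 5.2.1 applies the V2 baseline, "Change of plasma concentration versus baseline (i.e. change versus visit 2 values) will be computed for each study visit", and the Table 15 footnote does the same.

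**The concern.** There are two linked problems.

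First, CoQ10 is endogenous, so a subject's untreated level is needed to interpret anything measured after dosing, and it cannot be recovered once the first capsule is taken. Staff who work from the flow chart or from 10.5.1 could omit the PK tube at moment 0. Neither document allows imputation (Protocol 12.11, SAP 5.2.3). A subject without H0 drops out of the H0 rows of Tables 25 and 26 and out of Table 27 altogether.

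Second, V2 is the reference for the multidose rise but follows a study dose by 7 days. The documents give no half-life and no reason for 7 days; half-life is itself an outcome. If some of the Day -7 dose remains, V2 is too high and the percent rise in each arm is too small. V2 also serves as time 0 in the SAP's multidose half-life formula. The obvious check, V2 against V1-H0 in the same subjects, is not among the planned estimates.

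**Working it through.** **Step 1. The schedules side by side.**

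| Place | CoQ10 before the Day -7 dose? |
|---|---|
| Protocol 3.1 synopsis | not listed |
| Protocol 3.2 flow chart, Pharmacokinetics row | blank |
| Protocol 10.3 and 10.5.1 | not listed |
| SAP 4.5 | not listed |
| Protocol 10.6.11 | yes |
| SAP 4.3, 4.4, 5.2.3 | yes |
| SAP Tables 25 to 27 | yes |

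The flow chart's general Blood sampling row is marked at moment 0. That does not settle the matter. The laboratory tubes in Protocol 10.6.9 are separate from the 4 ml PK sample in 10.6.11, which has its own centrifuging and cryotubes.

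**Step 2. Where V1-H0 and V2 are reported.** V1-H0 appears in Tables 25 to 27 and Listing 24; V2 appears in Tables 13 to 15 and Listing 16. No table, model or interval uses both.

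**Step 3. Size of any carry-over.** The plan gives no figure to reproduce. The interval is 0 - (-7) = 7 days = 168 h. The fraction of the single-dose increment left at V2 is f = 2^(-168/half-life).

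Assumptions, none from the documents: half-life 24 to 120 h; endogenous level B = 0.8 microg/ml; single-dose increment I = 0.5 (range 0.3 to 0.8). From Protocol 6.2: levels C of about 2.5 (OD) and 3.5 microg/ml (BID). The residual is R = I x f, and the rise read from V2 is 100 x (C - B - R)/(B + R). The true rises are 100 x (2.5 - 0.8)/0.8 = 212.5% and 100 x (3.5 - 0.8)/0.8 = 337.5%.

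| Half-life | f | R at I = 0.5 | OD rise from V2 (I = 0.3 to 0.8) | BID rise from V2 (I = 0.3 to 0.8) |
|---|---|---|---|---|
| 24 h | 0.8% | 0.004 | 211% (210 to 212) | 335% (334 to 336) |
| 48 h | 8.8% | 0.044 | 196% (187 to 202) | 315% (302 to 323) |
| 72 h | 19.8% | 0.099 | 178% (161 to 191) | 289% (265 to 307) |
| 120 h | 37.9% | 0.189 | 153% (127 to 174) | 254% (217 to 283) |

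**Step 4. The half-life formula.** SAP 5.2.1 takes the rate constant as clearance/volume, with clearance = dose/AUC and volume = dose/C0, where C0 is V2 in the multidose phase. Dose cancels, leaving half-life = ln 2 x AUC/C(V2). Take OD with 2.5 at V3, V4 and V5.

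- Without carry-over, AUC = 7 x (0.8 + 2.5)/2 + 21 x 2.5 = 64.05 and AUC/C(V2) = 64.05/0.8 = 80.1 days.
- With R = 0.099, AUC = 7 x (0.899 + 2.5)/2 + 52.5 = 64.40 and AUC/C(V2) = 64.40/0.899 = 71.6 days.

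The computed half-life falls by about 10.5%.

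**Step 5. Between arms.** All 24 subjects take the same dose before randomisation at V2, so R is equal on average. The concentration difference (3.5 - 2.5) does not change. The gap in percentage points shrinks from 1.0/0.8 = 125 to 1.0/0.899 = 111 at 72 h, but neither arm is favoured.

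**Step 6. Precision of the missing check.** For V2 minus V1-H0 in 24 subjects, the half-width is t(23)/sqrt(24) times the SD of the paired difference: 0.35 SD for a 90% interval and 0.42 SD for 95%.

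**The case against.** **The baseline is deliberate.** A reader might infer that the SAP breaks its own definition by using V2. It does not: SAP 4.4 names V2 for the multidose phase in the very next sentence, and by counting first intake from the V2-V5 diary it makes V2 fit the general rule as well. There is some tension, because the Day -7 capsule is also study product, but no contradiction. This objection stands.

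**The pre-dose sample is planned.** A reader of the flow chart might infer that no untreated level is to be measured. The dedicated PK section and the SAP say otherwise, and the shorter passages list times after intake without excluding an earlier one. This stands too: the fault is inconsistency, and whether a site would miss the sample is a risk, not a certainty.

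**A raised V2 would be visible.** Table 13 (Total column) and Table 25 give the V2 and H0 means with intervals, and Listings 16 and 24 give individual values. So it is too strong to say that nothing planned could reveal carry-over. But comparing two separate intervals by eye ignores the pairing, and nothing commits the report to doing it.

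**The size is assumed, and the primary objective concerns the level reached.** Both true. With a short half-life the effect vanishes. The plan nonetheless reports the percent rise under its primary analysis.

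**The supplement exclusion is no benchmark.** The exclusion of "Intake of any food supplements within 2 weeks of the beginning of the study, except vitamin D and calcium" might be read as showing that 7 days is too short. It covers any supplement at unstated exposure and says nothing about clearance of one capsule.

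**Conclusion.** The point holds in two parts.

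The schedule conflict is a matter of fact and the more pressing part. Four protocol places and SAP 4.5 omit a sample that Protocol 10.6.11 and the SAP's single-dose analysis depend on. The loss would be Table 27 and the untreated level for each subject affected, at worst all 24.

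The baseline issue is a missing check, not a shown bias. If the Day -7 dose has not cleared, the within-arm percent rise is understated: negligibly at a half-life of about 24 h, materially at about 72 h or more (212.5% read as 178% under the central assumptions), with the multidose half-life pulled down by about a tenth. These figures rest on assumed half-life, endogenous level and increment. Drift in diet or assay between V1 and V2 could move V2 either way.

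A reader might go further and conclude that the wash-out is too short, or that the OD versus BID comparison is biased. The documents support neither: they give no half-life, and the common dose before randomisation should balance carry-over between arms.

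**What to change.** 1. Reconcile the flow chart, synopsis, Protocol 10.3 and 10.5.1 and SAP 4.5 with Protocol 10.6.11, so that the pre-dose PK sample appears in every schedule.
2. Add to SAP 5.2.1 the paired V2 minus V1-H0 difference in all subjects, with its confidence interval, as a descriptive wash-out check. State the interval level, since Protocol 12.1 uses 90% and SAP 5.2.1 uses 95%.
3. In Table 15, always show the multidose change from V1-H0 beside the change from V2. Do not let the result of the check decide which baseline is used: no margin is defined, and with 24 subjects the check may be inconclusive.

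The cost is some schedule wording, one extra estimate and one extra column. No sample is needed beyond the one Protocol 10.6.11 already provides for.

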6 INTRODUCTION

6.1 Background

Coenzyme Q10 (CoQ10) is a substance similar to a vitamin. It is found in every cell of the body. The body produces CoQ10, and the cells use it to produce energy for the body needs for cell growth and maintenance. It also functions as an antioxidant, which protects the body from damage caused by harmful molecules. CoQ10 is naturally present in small amounts in a wide variety of foods, but levels are particularly high in organ meats such as heart, liver, and kidney, as well as beef, soy oil, sardines, mackerel, and peanuts.

The Coenzyme Q10, also known as ubiquinone, is an endogenous molecule, synthesized by our body and essential for the proper functioning of the mitochondria, or the cellular units responsible for the production of energy in the body.

In organisms it participates in redox reactions and, depending on the state of oxidation, it can be present in three forms: an oxidized, a semi-quinone intermediate and a reduced form. The side chains make it very lipophilic, in fact it is present in biological membranes, especially mitochondrial ones.

Higher levels of Q10 could improve the efficiency of the electron transport chain, increasing the available energy.

Rebalancing the function of the mitochondria, which are in practice the "lungs" of every single cell, means allowing the cell to restore its original energy potential, and, in a certain sense, to "rejuvenate" allowing it to "breathe" and use the available energy correctly.

If coenzyme Q is reduced by acquiring an electron it forms a radical called ubisemichinone (QH.). For further reduction the compound becomes a ubiquinol (QH2).

The concentration of coenzyme Q10 tends to decrease with aging; low levels are also recorded in the presence of particular chronic diseases, such as those resulting from heart problems, Parkinson's disease, muscular dystrophy, diabetes, cancer and AIDS. Certain drugs, such as statins used in the control of hypercholesterolemia, can also lower Coenzyme Q10 levels.

Coenzyme Q10 has been shown to have beneficial effects on some patients with migraine and is a major component of the myth cocktail used in the treatment of mitochondrial myopathy and other metabolic disorders.

Taking 100 mg a day or more of CoQ10 has caused mild insomnia in some people. And research has detected elevated levels of liver enzymes in people taking doses of 300 mg per day for long periods of time. Liver toxicity has not been reported.

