12 BIOSTATISTICAL METHODS

12.1 General

Due to the explorative aim of the study, descriptive statistics and confidence intervals at 90% level will be provided.

In particular, continuous variables will be presented as arithmetic mean values \pm standard deviation (SD) and median values with interquartile range; geometric means will be provided as well; for categorical variables absolute and percentage frequencies will be provided.

All data collected during the study visits and up to V5 (EOS) will be presented for the two groups.

Any major deviations from this plan, the reasons for such deviations, and all alternative or additional statistical analyses that may be performed will be explained in the Statistical Analysis Plan (SAP), which will give a detailed technical description of all statistical analyses. All deviations and/or alterations will be summarized in the Clinical Study Report (CTR).

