4.1 General Methodology and Presentation of the Results

The default summary statistics for quantitative variables will be the number of observations (n), mean, standard deviation (SD), median, interquartile range, minimum (min) and maximum (max), for those subjects with data.

For qualitative variables, the number (n) and percentage (%) of subjects with non-missing data per category will be the default summary presentation, and where appropriate and present, the number of missing values as a “Missing” category.

Percentages will be calculated using a denominator of all subjects in a specified population or treatment group, unless specified otherwise. The denominator will be specified in a footnote to the tables for clarification if necessary.

Statistical Output Layout

Tables and listings exceeding one page should indicate “Page x of y” at the bottom of each page. The definition of baseline and endpoint value will be described in a footnote in every TLF where applicable.

All listings contain columns for subject screening number and treatment group.

The format for presentation of time variables will be hh:mm. The format for presentation of date variables will be dd/mm/yyyy.

Dates that are missing because they are not applicable for the subject will be presented as “N/A”, unless otherwise specified. Missing data will be represented on subject listings as “/” fields.

Listings will be sorted by subject screening number unless specified otherwise.

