Imputations for missing values: No imputation of missing data will be performed

Analysis Sets to be used for:	Tables	ITT and PP analysis set
	Listings	ITT analysis set
	Figures	ITT and PP analysis set

	Form	Form No.	1M-DMST-011-01-A1
	Statistical Analysis Plan	Page	Page 23 of 69
		Effective Date	07/05/2018

Primary efficacy variable will be summarized by treatment group as follows:

Table 13. Primary Efficacy Variable at Each Study Visit (ITT Analysis Set)

Default summary statistics per treatment group for the primary efficacy variable (Plasma concentration of Coenzyme Q10) at each study visit will be presented for the ITT analysis set.

This table will be replied on the PP analysis set.

Table 14. Plasma concentration of coenzyme Q10 by gender (ITT Analysis Set)

Default summary statistics per gender for the primary efficacy variable (Plasma concentration of Coenzyme Q10) at each study visit will be presented for the ITT analysis set.

This table will be replied on the PP analysis set.

Table 15. Change versus baseline by Treatment (ITT Analysis Set)

Default summary statistics per treatment group for the change versus baseline at each study visit will be presented for the ITT analysis set.

This table will be replied on the PP analysis set.

Table 16. Pharmacokinetic Parameters by Treatment (ITT Analysis Set)

Default summary statistics per treatment group for each pharmacokinetic parameter will be presented for the ITT analysis set.

This table will be replied on the PP analysis set.

Table 17. Confidence Interval and Results of T-test for Primary Efficacy Variable (ITT Analysis Set)

Confidence interval at 95% will be presented for the means of the pharmacokinetics parameters in the two groups in the ITT analysis set. The table also contains the result of the Student t-test detecting the differences between the two groups.

This table will be replied on the PP analysis set.

A Primary efficacy variable will be presented in subject data listings as follows:

Listing 16. Listing of Primary Efficacy Variable

A listing of the values for the primary efficacy variable (Plasma concentration of Coenzyme Q10) as used in the primary analysis, sorted by screening number and within subjects by time point will be presented.

Listing 17. Listing of Pharmacokinetic parameters

A listing of the values for the pharmacokinetic parameters as used in the primary analysis, sorted by screening number will be presented.

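### The OD-BID t-test on AUC_t and Cmax is unbiased but not adjusted for the endogenous V2 level, change is given only in percent, and the protocol's geometric means are missing from the SAP

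*SAP*

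**What the plan says.** **Baseline.** For the multidose phase, SAP 4.4 sets the reference: "baseline will be visit 2 (day 0) if not specified otherwise". Protocol 6.1 says that CoQ10 "is an endogenous molecule, synthesized by our body", so this value is a real concentration that differs between people. V2 sampling is scheduled for every subject.

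**Change.** SAP 5.2.1: "Change of plasma concentration versus baseline (i.e. change versus visit 2 values) will be computed for each study visit". The formula that follows is percent change only. For Table 15: "Default summary statistics per treatment group for the change versus baseline at each study visit will be presented". The template shows n, mean (SD), median and min/max by arm, without a confidence interval or test. Vital signs (SAP 5.2.2.2) get both absolute and relative change. The single-dose phase (SAP 5.2.3, Table 27) has its own percent change, from hour 0.

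**Between-arm comparison.** SAP 5.2.1: "A Student t-test for unpaired data will be performed in order to detect differences between the two groups in the pharmacokinetics parameters". These are AUC_t, Cmax, Tmax and half-life, untransformed: "terminal half-life will be presented descriptively on the original scale". Table 17 applies a 0.05 significance rule.

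**Geometric means.** Protocol 12.1: "geometric means will be provided as well". SAP 4.1 instead lists: "The default summary statistics for quantitative variables will be the number of observations (n), mean, standard deviation (SD), median, interquartile range", then minimum and maximum. No SAP method or table template contains a geometric mean, and SAP section 6 reports no departure from the protocol.

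**The concern.** The primary objective is to choose between OD and BID. The comparison rests on 12 subjects per arm, with no power calculation. Subjects enter the multidose phase with different CoQ10 levels of their own, and those levels probably carry through to the later visits. A test that leaves this variation in the error term gives wider intervals than the data already being collected would allow.

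The change summary raises a separate question. Dividing each rise by that subject's own V2 value and averaging arithmetically gives heavy weight to subjects with a low V2 value. In an arm of 12, one or two of them can move the mean noticeably. The geometric means in the protocol would have given a steadier summary, but they were not carried into the SAP.

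**Working it through.** The plan states no power, SD, CV, correlation or adult baseline level, so there is no planned figure to reproduce.

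**Inputs from the documents**
- 12 per arm, 1:1, randomised at V2 (SAP 2.3, 2.5).
- Visits at days 0, 7, 14 and 28 (SAP 4.3).
- Expected levels of about 2.5 µg/ml (OD) and 3.5 µg/ml (BID) (protocol 6.1).
- Significance at 0.05 (SAP Table 17); two-sided assumed.

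**Assumptions not in the documents**
- Lognormal baseline with mean 0.8 µg/ml and CV 30-50%.
- Correlation r between baseline and follow-up of 0.3-0.7.

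**1. Is the baseline really absent from the tested parameters?** Trapezoid weights in days are 3.5 (V2), 7 (V3), 10.5 (V4) and 7 (V5), total 28. V2 carries 3.5/28 = 12.5% of the AUC_t weight. It is also the time-0 concentration in the half-life formula. It is therefore present, but it is not adjusted for.

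**2. Is the planned difference biased?** No. Allocation is random, so V2 is balanced in expectation. For a single-visit concentration with a true difference of 3.5 - 2.5 = 1.0, the simulated mean unadjusted difference was 0.997-1.003.

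**3. Precision lost.** With V2 as covariate the error variance is multiplied by 1 - r². The unadjusted variance is larger by a factor 1/(1 - r²), before a small loss of degrees of freedom:
- r = 0.3: 1/0.91 = 1.10
- r = 0.5: 1/0.75 = 1.33
- r = 0.7: 1/0.51 = 1.96

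For a single-visit concentration, difference 1.0 and SD = CV × 3.0, power is:

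| CV (SD) | Unadjusted t | ANCOVA r = 0.3 | r = 0.5 | r = 0.7 |
|---|---|---|---|---|
| 30% (0.9) | 0.74 | 0.78 | 0.85 | 0.95 |
| 40% (1.2) | 0.50 | 0.53 | 0.61 | 0.78 |
| 50% (1.5) | 0.35 | 0.37 | 0.44 | 0.59 |

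At CV 40% the 95% half-width falls from 1.02 to 1.00, 0.90 or 0.75 µg/ml.

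**4. The parameter that the SAP tests.** Simulation of AUC_t over V2-V5, 12 per arm, with 60%, 90% and 100% of the rise assumed reached at V3, V4 and V5:

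| Response model | Planned t-test on AUC_t | ANCOVA on log AUC_t with log V2 |
|---|---|---|
| Proportional to baseline (log SD 0.25-0.4) | about 20-46% | about 49-87% |
| Additive (SD of rise 0.6-0.9 µg/ml) | about 59-92% | about 66-96% |

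**5. Mean percent change.** The rise in OD means is (2.5 - 0.8)/0.8 = 212%.
- *Additive response.* For a lognormal baseline, E[1/C0] = (1 + CV²)/mean. The expected mean percent change is 212.5% × 1.09 = 232% at CV 30% and 212.5% × 1.25 = 266% at CV 50%. Simulation gives 232-268%. If every subject rose by the same 1.7 µg/ml, the median would be 212.5% × √(1 + CV²), which is 222% and 238%, roughly half the excess.
- *Proportional response.* Percent change does not depend on baseline, and the mean stays at about 212%.
- *Lognormal at both times, equal CV, correlation r.* The mean ratio is inflated by exp(s²(1 - r)), with s² = ln(1 + CV²). At CV 40% and r = 0.5, s² = 0.148 and the factor is 1.077, so OD reads 3.125 × 1.077 - 1 = 237%. Over CV 30-50% and r 0.3-0.7 the OD mean is 221-265%, while the simulated median is 214-220%.

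**6. Geometric means.** Protocol 12.1 set beside SAP 4.1, Tables 13, 16, 25 and 28, and SAP section 6 shows the omission directly. No assumption is needed.

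**The case against.** A reader might infer that the plan overstates the difference between BID and OD, or that it ignores the baseline altogether. The documents support neither. Groups are randomised at V2, so the t-test difference is unbiased. V2 is the first AUC_t point and enters the half-life. Inflation can affect only a within-arm descriptive mean, and only if the response is not strictly proportional.

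That mean does not stand alone. Table 15 also gives the median, Table 13 gives V2 to V5 levels by arm with intervals, Listing 16 gives every value, and SAP 5.2.1 asks for outliers to be examined. Someone reading the whole output could see a low-baseline subject at work. No test is planned on percent change or on V5 concentration, so power for those analyses does not describe a planned comparison. The relevant figures are those for AUC_t.

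The gain may also be small. Under an additive response, an unadjusted t-test on the V5 level has about 64-95% power against 67-96% for log ANCOVA, which is almost nothing gained. The documents do not say which response model applies. Finally, the study is exploratory, and protocol 12.6 pre-specifies no hypothesis.

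All of this stands and limits the point to a loss of efficiency and gaps in reporting. It does not remove it. The SAP still prints p-values against 0.05 to help choose a regimen, the covariate is already scheduled, and the missing geometric means are a plain mismatch with the protocol.

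**Conclusion.** The point holds as one of precision and reporting, not of bias. The planned between-arm test is valid, but it leaves out a pre-randomisation measurement scheduled in every subject. The cost is 10% to 96% more variance as r goes from 0.3 to 0.7. For AUC_t this is power of about 20-46% instead of 49-87% under a proportional response, and 59-92% instead of 66-96% under an additive one. Those ranges depend on the assumed baseline, CV, time course and response model.

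The arithmetic mean percent change may read up to about 268% where the means rise by 212%, or may show no inflation at all. The median is less affected. The absence of geometric means, against SAP section 6, is certain. In an exploratory study the consequence is moderate, but the change should be made because it needs no new data.

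**What to change.** 1. **SAP 5.2.1 and Table 17.** Compare BID with OD by ANCOVA on log AUC_t and log Cmax, with log V2 concentration as covariate. Report the adjusted geometric mean ratio with its confidence interval. Give the same analysis of log V5 concentration as support.
2. **Tables 13, 16, 25 and 28.** Add geometric means for concentrations, AUC_t and Cmax, as protocol 12.1 promises. If any are left out on purpose, say so in SAP section 6.
3. **Tables 15 and 27.** Report the geometric mean ratio to baseline with its confidence interval, and the absolute change. Keep percent change as median with interquartile range.
4. **Confidence level.** State one level for these intervals; protocol 12.1 has 90% and SAP 5.2.1 has 95%.

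The cost is SAP wording and code, with no new samples or visits. The small downside is that results are read as ratios of total concentration, endogenous part included. With the protocol's levels, 3.5/2.5 = 1.40, whereas after subtracting an assumed baseline of 0.8 the ratio is 2.7/1.7 = 1.59. The absolute change in item 3 lets the reader see both.
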